7.2.2.2. ESSDAI total score

ESSDAI total score is calculated in the ClinTrial database as the weighted sum of the 12 domains (one decimal will be kept). The maximum theoretical score is 123. If one item is missing, then the total score is not calculated.

7.2.2.3. ESSPRI total score

The ESSPRI total score is derived as the mean of the 3 items (one decimal will be kept). If one item is missing, then the total score is not calculated. The maximum theoretical score is 10 (mean score of the 3 subscores).

7.2.2.4. STAR score

The STAR score (Sjogren's Tool for Assessing Response) is a composite responder index in primary Sjögren's syndrome (pSS). This score will not be computed in the ClinTrial database and will have to be derived. The STAR score should be calculated as follows:

- Systemic activity (/3points):
 - **3 points** if decrease of at least 3 points in clinESSDAI from baseline.
 - **0 points** otherwise.
- Patient reported outcome (/3points):
 - **3 points** if decrease of at least 1 point or at least 15% in ESSPRI from baseline.
 - **0 points** otherwise.
- Lachrymal gland function (/1point):
 - If abnormal Schirmer's test score at baseline (*i.e.* < 5 mm).
 - **1 point** if increase of at least 5mm from baseline (on mean of both eyes).
 - **0 point** otherwise.
 - If normal Schirmer's test score at baseline:
 - **1 point** if no change to abnormal value (on mean of both eyes).
 - **0 point** otherwise.
 - Or**
 - If abnormal OSS score at baseline (*i.e.* ≥ 3):
 - **1 point** if decrease of at least 2 points from baseline (on mean of both eyes).
 - **0 point** otherwise.
 - If normal OSS test score at baseline:
 - **1 point** if no change to abnormal value (on mean of both eyes).
 - **0 point** otherwise.
- Salivary gland function (/1point):
 - If unstimulated salivary flow score is > 0 at baseline:
 - **1 point** if increase of at least 25% from baseline.
 - **0 point** otherwise.
 - If unstimulated salivary flow score is equal to 0 at baseline:
 - **1 point** if any increase from baseline.
 - **0 point** otherwise.
- Biological (/1point):
 - **1 point** if decrease of at least 10% of serum IgG level or decrease of at least 25% of RF level.
 - **0 point** otherwise.

For the Lachrymal gland function domain, if the amelioration criterion is met for at least one of the two scores (Schirmer or OSS) on the mean of the two eyes then patient get 1 point for this domain. The STAR score is then the sum of the 5 previously mentioned domains. Finally, a patient is a candidate STAR responder if his STAR score is ≥ 5 .

ClinESSDAI is defined as a sub score of the ESSDAI score taking into account all ESSDAI domains except the Biological one and considering new weights. The new weights for calculation of clin ESSDAI are: 4 for Constitutional domain, 4 for Lymphadenopathy domain, 2 for Glandular domain, 3 for Articular domain, 3 for Cutaneous domain, 6 for Pulmonary domain, 6 for Renal domain, 7 for Muscular domain, 5 for PNS domain, 5 for CNS domain, and 2 for Haematological domain.

If one domain cannot be calculated, then the STAR score will not be calculated. However, for the definition of responder:

- If the sum of the non-missing items ≥ 5 , then the patient will be considered as responder.
- If the sum of the non-missing items + maximal potential sum of the missing items < 5 then the patient will be considered as non-responder.

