5. INCLUSION AND WITHDRAWAL OF PATIENTS

5.1. Inclusion criteria

All patients included should present the following characteristics:

1. Male or female aged between 18 to 75 years (both inclusive),
2. Patients must have a body mass index (BMI) of 18 (exclusive)-40 (inclusive),
3. Diagnosis of primary Sjögren's Syndrome based on 2016 ACR-EULAR criteria ([Appendix 2](#)),
4. ESSDAI total score ≥ 6 during screening, with at least 6 points scored within the 7 following domains: constitutional, lymphadenopathy, glandular, articular, cutaneous, hematologic and biologic,
5. Positive anti-SSA (Ro) antibodies or anti-nuclear antibodies (ANA) $\geq 1:320$ or rheumatoid factor (RF) > 20 IU/ml during screening period, measured in a central laboratory,
6. Stimulated whole salivary flow rate > 0 mL/minute,
7. Negative Tuberculosis test (Quantiferon or T-Spot test) during screening,
8. A chest x-ray obtained during the screening period or anytime within 90 days prior to signing the ICF with no evidence of current active infection (e.g. TB), malignancy, or clinically significant abnormalities (unless due to pSS),
9. All vaccinations deemed necessary by the investigator for the patient, up to date,
10. Female patient is postmenopausal, surgically sterile (having had a hysterectomy or bilateral oophorectomy) and/or is using a highly effective method of contraception (described in [Section 5.3](#)) until the last follow-up visit. In case of use of oral contraception women should have been stable on the same contraceptive drug for at least 3 months prior to the first IMP administration,
11. Non-vasectomized male patients having a female partner of childbearing potential must agree to the use of a highly effective method of contraception from first IMP administration until the last follow-up visit,
12. Willing to adhere to the prohibitions and restrictions specified in this protocol,
13. Signed written informed consent (obtained as described in [Section 13.3](#) of the protocol).

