4.3.5. Additional estimand based on CRESS

This estimand aims at evaluating the effect of the treatments on the Composite of Relevant Endpoints in Sjögren's Syndrome (CRESS): a composite score, in all patients assuming non-occurrence of IEs. The motivation for this choice is the same as the primary estimand.

The attributes of these estimands are defined as follows:

- Treatment: S95011 or placebo.
- Population: RS.
- Variable 1: proportion of responders in CRESS at W013 defined as patients with a response on ≥ 3 of the 5 items.
- Summary measure: difference in proportion between treatments.
- Intercurrent events (IE):
 - IE1: Study drug discontinuation for major worsening of primary Sjögren's syndrome.
 - IE2: Increase or initiation of authorized medication for pSS.

- IE3: Study drug discontinuation for AE related to study drug.
- IE4: Study drug discontinuation for other reasons (non-medical reason, AE not related...).
- IE5: Switch of treatment group (error of dispensation).
- IE6: Decrease or stop of authorized medication for pSS.

Note: In case a patient is concerned by several IEs, the first event will be considered. If several IE occurred the same day, IE will be considered to be more conservative in the following order: IE1; IE2; IE3; IE4; IE5, IE6. S95011 will be compared to placebo on the responders in the RS using a logistic regression model including the fixed, categorical effect of treatment and randomization stratification factors (*rando_factor*).

LOGISTIC REGRESSION MODEL:

$$\text{responder} = \text{rando_factors treatment} \quad [4]$$

The assumptions underlying the model, as for instance, independence of errors, linearity in the logit for continuous variables, absence of multicollinearity, and lack of strongly influential outliers will be checked.

If the model is not running due to too few patients in the stratas, the model mentioned above will be modified. Thus, the two stratification factors in the model will be replaced by the following composite factor: baseline intake of oral corticosteroids or antimalarial or both (yes/no). If the model is still not running with the stratification factor in two classes, then the stratification factor will not be considered.

The handling of IEs and missing data will be in the same line as the primary analysis of the primary estimand, but imputation will be done directly on the response variable. Sensitivity and supplementary analyses are not planned for this estimand.

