7.2.2.5. CRESS score

The CRESS score (Composite of Relevant Endpoints in Sjögren's Syndrome) is a composite responder index in primary Sjögren's syndrome (pSS). This score will not be computed in the ClinTrial database and will have to be derived.

The CRESS score should be calculated as follows:

- Systemic activity (/1points):
 - **1 point** if clinESSDAI score at visit is < 5 .
 - **0 points** otherwise.
- Patient reported outcome (/1points):
 - **1 point** if decrease of at least 1 point or at least 15% in ESSPRI from baseline.
 - **0 points** otherwise.
- Tear gland function (/1point):
 - If abnormal Schirmer's test score at baseline (*i.e.* < 5 mm):
 - **1 point** if increase of at least 5mm from baseline (on mean of both eyes).
 - **0 point** otherwise.
 - If normal Schirmer's test score at baseline:
 - **1 point** if no change to abnormal value (on mean of both eyes).
 - **0 point** otherwise.

Or

 - If abnormal OSS score at baseline (*i.e.* ≥ 3):
 - **1 point** if decrease of at least 2 points from baseline (on mean of both eyes).
 - **0 point** otherwise.
 - If normal OSS test score at baseline:
 - **1 point** if no change to abnormal value (on mean of both eyes).
 - **0 point** otherwise.
- Salivary gland function (/1point):
 - If unstimulated salivary flow score is > 0 at baseline.
 - **1 point** if increase of at least 25% from baseline.
 - **0 point** otherwise
 - If unstimulated salivary flow score is equal to 0 at baseline:
 - **1 point** if any increase from baseline.
 - **0 point** otherwise.
- Serological (/1point):
 - **1 point** if decrease of at least 10% of serum IgG level or decrease of at least 25% of RF level.
 - **0 point** otherwise.

For the Tear gland function domain, the patient is responder if the amelioration criterion is met for at least one of the two scores (Schirmer or OSS) on the mean of the two eyes. The CRESS score is then the sum of the 5 previously mentioned domains. Finally, a patient is a candidate CRESS responder if his CRESS score is ≥ 3 .

ClinESSDAI is defined in the previous section.

If one domain cannot be calculated, then the CRESS score will not be calculated. However, for the definition of responder:

- If the sum of the non-missing items ≥ 3 , then the patient will be considered as responder.
- If the sum of the non-missing items + maximal potential sum of the missing items < 3 then the patient will be considered as non-responder.

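### The CRESS systemic item is a state at the visit that some patients may already meet at baseline, yet the CRESS responder model, unlike the ESSDAI and ESSPRI responder models, has no baseline term

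*SAP*

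**What the plan says.** **Scoring.** SAP 7.2.2.4 (STAR) and 7.2.2.5 (CRESS) each use five domains.

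- **Systemic item.** STAR gives 3 points "if decrease of at least 3 points in clinESSDAI from baseline", which is a change rule. CRESS gives 1 point "if clinESSDAI score at visit is < 5", which makes no reference to baseline.
- **Tear item (1 point in both).** A test that is abnormal at baseline must improve; a test that is normal at baseline need only not become abnormal. One test is enough. STAR: "For the Lachrymal gland function domain, if the amelioration criterion is met for at least one of the two scores (Schirmer or OSS"), the point is given. CRESS: "the patient is responder if the amelioration criterion is met for at least one of the two scores".
- **Other items.** ESSPRI ("if decrease of at least 1 point or at least 15% in ESSPRI from baseline"), unstimulated salivary flow, and IgG or RF are change rules in both indices.
- **Thresholds.** "Finally, a patient is a candidate STAR responder if his STAR score is ≥ 5". For CRESS the threshold is 3.

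**Entry.** Protocol 5.1 requires "ESSDAI total score ≥ 6 during screening, with at least 6 points scored within the 7 following domains", and the biological domain is one of the seven. SAP 7.2.2.4 defines clinESSDAI without that domain and with new weights.

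**Models.** SAP 4.3.5 analyses CRESS response "using a logistic regression model including the fixed, categorical effect of treatment and randomization stratification factors". This is model [4], and STAR uses it too (4.3.4). Model [2] (4.3.1.3) adds the baseline score, and model [3] (4.3.3) adds baseline ESSDAI and baseline ESSPRI. SAP 7.3.2 describes the responder model in general as having a baseline covariate, and its example code contains one. SAP section 6 explains why CRESS was added but not why its model has no baseline term.

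**The concern.** A threshold on a final value depends on where the patient started. The entry score counts a domain that clinESSDAI drops, so a patient can be eligible and already satisfy the CRESS systemic item. Baseline for clinESSDAI is the W000 value (SAP Table (7.1.1) 1), up to 28 days after the qualifying ESSDAI. Protocol 5.1 sets the ESSDAI threshold during screening only, so baseline may be lower still. SAP 4.1.3 itself provides a baseline ESSDAI class below 5.

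Baseline clinESSDAI should therefore be a strong predictor of this CRESS item, and it is the covariate missing from the model. The ESSDAI and ESSPRI responder analyses do adjust for their own baselines. With a 2:1 allocation and about 15 placebo patients, a chance difference in baseline disease activity passes into the CRESS result unadjusted. CRESS is tested inferentially under a stated secondary objective, so this bears on a reported treatment comparison, though not on the primary one.

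**Working it through.** The plan gives no power or response-rate figure for CRESS or STAR, so there is none to reproduce. The check has four steps.

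**1. What a responder must have met.** I enumerated the 32 met/not-met patterns of the five domains.

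- CRESS (1 point each, threshold 3): the two items that can be held without change (systemic, tear) give at most 2. A responder must meet at least 3 - 2 = 1 change rule.
- STAR (3 + 3 + 1 + 1 + 1, threshold 5): only the tear item can be held without change, giving at most 1. The other 4 points need at least two change rules, for example ESSPRI (3) plus saliva (1), and at least one of the two must be clinESSDAI or ESSPRI.
- Tear example for both indices: mean Schirmer 4 to 0 mm with mean OSS 1 to 2 earns the point, because OSS stays below 3.

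**2. Who meets the CRESS systemic item at entry.** The inputs are the ESSDAI weights (Protocol Appendix 3) and the clinESSDAI weights (SAP 7.2.2.4). Over all level combinations of the seven entry domains, exactly four profiles have ESSDAI >= 6 and clinESSDAI < 5. All four have biological level 2 (2 × 1 = 2 ESSDAI points, 0 in clinESSDAI):

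| Added to biological level 2 | ESSDAI | clinESSDAI |
|---|---|---|
| lymphadenopathy level 1 | 4 + 2 = 6 | 4 |
| glandular level 2 | 4 + 2 = 6 | 4 |
| haematological level 2 | 4 + 2 = 6 | 4 |
| glandular level 1 and haematological level 1 | 2 + 2 + 2 = 6 | 4 |

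Activity in any of the other five domains adds at least 5 to clinESSDAI, so it creates no further cases. With the levels printed in Appendix 3, these are 4 of 5,146 eligible profiles. That is a count of patterns, not a prevalence, and the documents give no prevalence.

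**3. How strongly baseline predicts the item.** Assumption: the change in clinESSDAI is normal with mean m and SD s. Then P(clinESSDAI < 5 at W013) = Φ((5 - b - m)/s) for baseline b. The documents give no figures for clinESSDAI; the SDs of 4 to 6 are those quoted for ESSDAI change in Protocol 10.2, and m is assumed.

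| m, s | b = 4 | b = 9 | b = 14 |
|---|---|---|---|
| 0, 4 | 60% | 16% | 1% |
| 0, 6 | 57% | 25% | 7% |
| -2, 4 | 77% | 31% | 4% |
| -2, 5 | 73% | 34% | 8% |
| -2, 6 | 69% | 37% | 12% |

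The gradient is steep in every row.

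**4. What this does to CRESS response and balance.** Assumption: each of the three change rules is met by chance, independently, with probability p.

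| Status points held | Formula | p = 0.1 | p = 0.2 | p = 0.3 |
|---|---|---|---|---|
| both | 1 - (1 - p)³ | 27% | 49% | 66% |
| one | 3p²(1 - p) + p³ | 2.8% | 10% | 22% |
| neither | p³ | 0.1% | 0.8% | 2.7% |

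The top row takes the systemic point as certain. Using 73% for that point at p = 0.3, the 66% becomes 0.73 × 0.657 + 0.27 × 0.216 = 54%.

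For chance imbalance with 30 and 15 patients, the standard error of the arm difference in mean baseline is √(1/30 + 1/15) = 0.32 baseline SDs. A gap larger than half an SD arises with probability 2 × (1 - Φ(0.5/0.316)) = 11%.

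**The case against.** STAR and CRESS are named composite indices. Keeping a normal test normal and reaching a low-activity state are defensible design choices. The SAP cites no source for either index, so a departure from a published definition cannot be shown, and rewriting the items would harm comparability. This stands. Giving the tear point only for improvement on an abnormal test, or for both tests staying normal, would also still credit a maintained normal state.

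Much is already visible. SAP 4.3.7 plans STAR and CRESS by domain, clinESSDAI value and change by arm, and Schirmer class shifts. SAP 4.3.6 models Schirmer and OSS change separately. This also stands: imbalance and tear worsening can be seen at group level. Seeing an imbalance is not adjusting for it, however.

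Baseline clinESSDAI covers only one of five CRESS items, and another term in a small logistic model has a cost; the SAP already needs fallbacks for sparse strata. This is fair, but the term is one continuous covariate, and models [2] and [3] carry one and two such terms in the same sample.

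A reader might go further and infer that responders need not have improved at all. Step 1 rules that out for both indices. A reader might also infer that points held from baseline must dilute the treatment difference. That is not general: with assumed item probabilities of 0.30 on placebo and 0.45 on active, the difference in CRESS response is 0.244 with no held point, 0.261 with one and 0.177 with two.

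**Conclusion.** The point holds as a cheap improvement to a secondary endpoint. The CRESS systemic item is a state, a few minimum-entry profiles already meet it, and baseline clinESSDAI predicts it strongly across the assumed range. Model [4] leaves baseline out without a stated reason, against models [2] and [3] and against SAP 7.3.2.

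The omission does not bias the comparison and does not change who counts as a responder; randomisation protects the contrast. What is lost is precision and protection against chance imbalance with about 15 placebo patients. The size of that loss cannot be stated, because the documents give no distribution of baseline clinESSDAI. The probabilities in steps 3 and 4 show direction and steepness under assumed values and are not forecasts. The primary ESSDAI analysis is unaffected.

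The tear rule needs no change. It does limit interpretation: neither a CRESS nor a STAR response implies better tear function, and a CRESS response does not by itself imply lower systemic activity.

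**What to change.** In SAP 4.3.5, give CRESS its own model: responder = baseline clinESSDAI (continuous), stratification factors, treatment. Keep the existing fallback for sparse strata, and keep baseline clinESSDAI in the model if the stratification factor is collapsed or dropped. This brings 4.3.5 into line with 7.3.2. Because STAR also uses model [4], 7.3.2 should say that its baseline term does not apply there.

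Leave the STAR and CRESS scoring rules as they are. A table of tear response counting improvement only could be added as an optional supplementary description.

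Cost: one more term in a small logistic model, a line of SAP text and minor programming. Baseline clinESSDAI is derived from data already collected. The difference in proportions, computed as in 7.3.2, would then refer to a patient at the baseline value entered in the contrast, and the table should say so.

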7.2.2.5. CRESS score

The CRESS score (Composite of Relevant Endpoints in Sjögren's Syndrome) is a composite responder index in primary Sjögren's syndrome (pSS). This score will not be computed in the ClinTrial database and will have to be derived.

The CRESS score should be calculated as follows:

- Systemic activity (/1points):
 - **1 point** if clinESSDAI score at visit is < 5 .
 - **0 points** otherwise.
- Patient reported outcome (/1points):
 - **1 point** if decrease of at least 1 point or at least 15% in ESSPRI from baseline.
 - **0 points** otherwise.
- Tear gland function (/1point):
 - If abnormal Schirmer's test score at baseline (*i.e.* < 5 mm):
 - **1 point** if increase of at least 5mm from baseline (on mean of both eyes).
 - **0 point** otherwise.
 - If normal Schirmer's test score at baseline:
 - **1 point** if no change to abnormal value (on mean of both eyes).
 - **0 point** otherwise.

Or

 - If abnormal OSS score at baseline (*i.e.* ≥ 3):
 - **1 point** if decrease of at least 2 points from baseline (on mean of both eyes).
 - **0 point** otherwise.
 - If normal OSS test score at baseline:
 - **1 point** if no change to abnormal value (on mean of both eyes).
 - **0 point** otherwise.
- Salivary gland function (/1point):
 - If unstimulated salivary flow score is > 0 at baseline.
 - **1 point** if increase of at least 25% from baseline.
 - **0 point** otherwise
 - If unstimulated salivary flow score is equal to 0 at baseline:
 - **1 point** if any increase from baseline.
 - **0 point** otherwise.
- Serological (/1point):
 - **1 point** if decrease of at least 10% of serum IgG level or decrease of at least 25% of RF level.
 - **0 point** otherwise.

For the Tear gland function domain, the patient is responder if the amelioration criterion is met for at least one of the two scores (Schirmer or OSS) on the mean of the two eyes. The CRESS score is then the sum of the 5 previously mentioned domains. Finally, a patient is a candidate CRESS responder if his CRESS score is ≥ 3 .

ClinESSDAI is defined in the previous section.

If one domain cannot be calculated, then the CRESS score will not be calculated. However, for the definition of responder:

- If the sum of the non-missing items ≥ 3 , then the patient will be considered as responder.
- If the sum of the non-missing items + maximal potential sum of the missing items < 3 then the patient will be considered as non-responder.

7.2.2.6. MFI total score

The MFI (Multidimensional Fatigue Inventory) is a self-report measure designed to evaluate five dimensions of fatigue: general fatigue, physical fatigue, reduced motivation, reduced activity, and mental fatigue.

The MFI is a 20-item scale ranging from 1 to 5 to indicate how aptly certain statements regarding fatigue represent the individual experiences. For each of the 5 scales (general fatigue, physical fatigue, reduced activity, reduced motivation, and mental fatigue) a total score is calculated by summation of the scores of the individual items. Scores can range from the minimum of 4 to the maximum of 20. Higher total scores correspond with more acute level of fatigue.

Each of the 5 dimensions will be described but the total score will not be considered as not recommended.

Before calculating total scores of each of the 5 scales, one need to be careful about some items that have to be recoded. Indeed, as written above, higher total score of a specific domain correspond with more acute level of fatigue. Nevertheless, some items are coded reversely. For example, item 2 “Physically, I feel only able to do a little” is scored 1 for “yes, that is true” and 5 for “No that is not true”. Thus, for this item, a higher score is associated to a less acute level of fatigue. This is the case for items 2, 5, 9, 10, 13, 14, 16, 17, 18 and 19. For those 10 items, scores will be recoded as follows: 1=5, 2=4, 3=3, 4=2, 5=1.

Once the 10 reverse items have been recoded, the 5 scales total scores can be calculated as follows:

- General Fatigue is the sum of the patient’s score on items 1, 5, 12 and 16.
- Physical Fatigue is the sum of the patient’s score on items 2, 8, 14 and 20.
- Reduced activity is the sum of the patient’s score on items 3, 6, 10 and 17.
- Reduced Motivation is the sum of the patient’s score on items 4, 9, 15 and 18.
- Mental Fatigue is the sum of the patient’s score on items 7, 11, 13 and 19.

